1. OBJECTIVES

1.1 Specific Aims

Aim 1: Test the effectiveness of an EHR-based Medication Complete Communication (EMC2) strategy to improve patient understanding of medication risks, patients’ demonstrated safe use, and the detection of patients’ adverse drug events.

Aim 2: Assess whether the EMC2 Strategy can reduce disparities in understanding and demonstrated safe use by patient literacy level, English proficiency, and age compared to usual care.

Aim 3: Evaluate the effectiveness and fidelity of the EMC2 Strategy to promote provider counseling, deliver patient Rx information, monitor use, and inform providers of potential harms.

Aim 4: Explore patient, provider, and health system barriers to implementation and effectiveness.

Aim 5: Determine the cost of delivering the EMC2 strategy from a health system perspective.

1.2 Hypotheses

Related to Aim 1, we hypothesize that:

H1: Patients receiving the EMC2 intervention will have better understanding of medication risks than those in the control arm.

H2: Patients receiving the EMC2 intervention will demonstrate safer use of their medication than those in the control arm.

STU#: 00201638

H3: Adverse drug events will have a higher rate of detection for patients in the EMC2 intervention arm than in the control arm.

Related to Aim 3, we hypothesize that compared to usual care, patients receiving the EMC2 strategies will:

H4: Report higher rates of provider Rx counseling

H5: Report higher rates of receipt of print Rx information.

H6: Be more likely to communicate Rx questions.

H7: Report a greater frequency of clinic follow-up.

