9.4 Data Sources

Data sources for this study will include phone interviews with participants, data from participant responses to the IVR call, and survey responses from providers.

Data collected. The following measures, including covariates, effectiveness and fidelity outcomes, are described below.

Patient Covariates. Baseline assessment will include socio-demographics, social support, English proficiency, country of origin, health status, including number of comorbidities, and cognitive function (assessed by the Mini-Mental Status Exam). We will also probe for medication concerns (i.e. about costs, side effects, risks) for patients who do not fill or are not taking their medicine. We will assess health literacy via the Newest Vital Sign (NVS). Patients are given a copy of a nutrition label and asked 6 questions about how they would interpret and act on the information. Scores are classified as high likelihood of limited literacy (0-1), possibility of limited literacy (2-3), and adequate literacy (4-6). The NVS has a high correlation with the Test of Functional Health Literacy in Adults (TOFHLA) takes less time to administer, is validated in Spanish and includes numeracy items.

Patient Motivation. The Consumer Health Activation Index (CHAI) assesses participants' 'activation' or motivation to participate in healthcare decisions and actions.

Effectiveness Outcomes: Medication Knowledge. Medication-specific knowledge measures will be created per high-risk medication. Similar items will be made standard across drugs, related to 1) decision making prior to use, 2) risks and benefits, and 3) side effects. Correct answers will be

STU#: 00201638

tailored to the available content included in each Med Guide Summary, as done previously by our team. Total scores range from 0-100, calculated reflecting the % correct of total possible points for each medication.

Medication Behavior. We will assess medication behavior by three domains: fill, proper use, and actual use.

- Fill will be assessed by patient self-report (yes/no) of having attained the medication from the pharmacy.
- Proper Use, measured as yes/no per medication, will be assessed by requiring patients to properly indicate the correct indication, dose (# pills each time), frequency (times per day), and total pills per day.
- Adherence will be measured via the ASK-12 that includes 12 items assessing general medication attitudes and beliefs as well as, specific behaviors within the past 3 months.

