Adverse Drug Events (ADE). ADEs will first be assessed using a validated questionnaire administered by the RA during the 3-month follow-up phone call. If the patient reports that their medication is finished at the 1-month interview, the ADEs will be assessed using the same approach at the 1-month interview. [name] will review all self-reported ADEs to determine whether these symptoms could reasonably be linked to one of the prescribed high-risk medications. We will then determine whether confirmed ADEs were reported to the clinic via the IVR system by reviewing IVR data. Drs. [name] and [name] will oversee this process.

Fidelity Outcomes:

- Provider Counseling. We will ask patients (yes/no) whether their prescriber/nurse/pharmacist counseled them. We will also ask the Health Literacy supplemental items of the Consumer Assessment of Health Providers Survey (CAHPS) to evaluate the extent and quality of provider verbal counseling on Rx medications. Prescriber/nurse counseling will be assessed immediately following the appointment (during the baseline interview); pharmacist counseling will be assessed at baseline if the prescription has been filled by that time, otherwise on the 4-week call.
- Receipt of Med Guide Summaries. We will ask patients in both arms whether they received any written information from their provider.
- Receipt of IVR Calls and Nurse Counseling. We will collect data from the IVR to determine whether interviews were completed and whether responses warranted nurse counseling.
- Frequency of Clinic Follow-Up. We will ask patients (yes/no) whether someone from the clinic contacted them following any concerns reported to the IVR system.
- Helpfulness of EMC2 components. Intervention patients will be asked (yes/no) whether they received Med Guide Summaries, IVR calls, and follow-up nurse calls and how helpful they were. "On a scale of 1 to 10, 1 being not helpful at all and 10 being extremely helpful, how helpful was...?"
- Provider experience. We will ask providers at intervention clinics about their use of the BPA pop-ups (if they saw them and if so, how they used them), med sheets (if they noticed patients receiving them), and IVR (if they received any feedback from the patients about the call and if they saw any of the IVR reports).

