To account for the correlated nature of the data from participants at the same practice and multiple observations per patient, we will use GLMMs for analyses of all data, specifying identity link for continuous and the logit link for binary outcomes using PROC GLIMMIX in SAS (v.9.4). Treatment assignment by time will be the independent variable of primary interest and modeled as a fixed effect and practice location as a random effect, with additional subject statement to model correlations within patient. We will also include fixed effects for any potential confounding covariates noted in the descriptive studies. For all GLMM analyses we will report point estimates and 95% confidence

STU#: 00201638

intervals, and the extent to which random effects suggest correlation of outcomes within practice location. Additionally, we will estimate the ICCs for all outcomes to be used in future studies.

Aim 2 Analysis Plan: We will repeat all GLMM analyses described in Aim 1, but with the inclusion of a fixed effect for participants' literacy defined as limited (inadequate or marginal literacy) vs. adequate. We will formally test for differences in intervention effects according to literacy by including a literacy-intervention interaction term. Statistically significant interaction terms ($p < 0.05$) will indicate that the disparities in understanding between the intervention and usual care group vary by literacy level. Similar analyses will be used to test for interactions of intervention effects by age and English proficiency (using Census criteria of 'very well' vs. 'less than very well').

Aim 3 Analysis Plan: Following completion of enrollment, we will determine the extent to which the intervention was implemented as planned in the intervention arm. We will ask patients in the intervention arm if they were counseled, and whether they received the Med Guide Summaries and the post-visit IVR call. Bivariate analyses will be performed to compare relevant outcomes for H4-H7 between arms using t-tests, Wilcoxon Rank-Sum, or χ^2 tests, as appropriate. Aim 3 findings will also directly inform follow-up qualitative investigations in Aim 4.

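### H6 (patients more likely to communicate prescription questions) is assigned a between-arm test, but section 9.4 describes no measure of it in both arms

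*Combined protocol and SAP*

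**What the plan says.** Section 1.2 opens the Aim 3 hypotheses with "Related to Aim 3, we hypothesize that compared to usual care, patients receiving the EMC2 strategies will" and lists H4 to H7. The third is "H6: Be more likely to communicate Rx questions". It does not say to whom, over what period, or how this is recorded.

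The Aim 3 plan in section 11.1 states: "Bivariate analyses will be performed to compare relevant outcomes for H4-H7 between arms using t-tests", Wilcoxon rank-sum or chi-square tests as appropriate. It does not name the outcome variables.

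Section 9.4 sets out what is collected. On sources: "Data sources for this study will include phone interviews with participants, data from participant responses to the IVR call, and survey responses from providers". On content: "The following measures, including covariates, effectiveness and fidelity outcomes, are described below". Under the fidelity outcomes it says, for example, "We will ask patients (yes/no) whether their prescriber/nurse/pharmacist counseled them", and "We will also ask the Health Literacy supplemental items of the Consumer Assessment of Health Providers Survey (CAHPS) to evaluate the extent and quality of" the provider's spoken counseling about the medication.

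**The concern.** A hypothesis with a stated comparator and a stated test needs a variable collected the same way in both arms. H6 appears to lack one. An analyst who reached the end of the trial with only the described data would have to drop H6, choose a stand-in after seeing the data, or use IVR responses that only one arm was prompted to give.

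The matter has some weight in the plan's own reasoning. Section 2.1 cites a study in which 37% of ameliorable adverse drug events were attributed to patients not telling their provider about signs and symptoms, and section 9.2 has the IVR tell callers to ring the clinic directly if they are worried. Whether patients speak up is therefore a step on the path to earlier detection. A question not asked during follow-up cannot be recovered once follow-up has closed.

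**Working it through.** No arithmetic applies, and section 11.2 gives no figure for H6. The check sets each Aim 3 hypothesis beside the measures in section 9.4.

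- **H4, provider counseling:** a yes/no item on counseling by prescriber, nurse or pharmacist, plus the CAHPS items. Measured.
- **H5, printed information:** an item on written information from the provider, stated to be asked in both arms. Measured.
- **H6, communicating questions:** no item, time point or coding.
- **H7, clinic follow-up:** a yes/no item on contact by the clinic. An item exists, but its wording ties it to concerns given to the IVR, which usual-care patients are not prompted to use. That is a separate difficulty.

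Next, could anything else that is described stand in for H6?

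- **CAHPS items (9.4).** Their stated purpose is to rate the provider's counseling. That is provider behaviour and belongs to H4.
- **CHAI (9.4).** It measures a general disposition to take part in health care, not whether a question about this drug was put to anyone.
- **Probe for medication concerns (9.4).** It is not restricted by arm, but it covers only patients who do not fill or are not taking the drug, and it records what they tell the research assistant rather than the care team.
- **IVR responses (9.2, 9.3).** Answers are yes, no or do not know to scripted items, and prompts go only to the intervention arm. Used as the H6 outcome, the usual-care value would be absent or zero by construction, and the comparison would favour EMC2 whatever patients did.
- **Provider survey (3.2, 9.3, 9.4).** It goes only to intervention-clinic providers and asks about the tools.
- **Medical charts.** Section 25.3 says the research team will have no access to records, and section 9.4 does not list charts as a source. Section 11.2, however, defines detection of adverse drug events by what is recorded in the chart. The documents conflict on chart use, and neither passage describes chart extraction of patient questions.

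Result: three of the four hypotheses have a labelled item, and H6 has neither an item nor an adequate substitute among the measures described.

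**The case against.** The strongest objection is that the interview instruments are not in the documents. Section 9.4 describes measures in summary and does not say that its list is complete. Section 22.4 mentions several additional measures, unnamed, that move to an earlier interview when that one becomes final. The CAHPS item wording is not given either, so an individual item might touch on patients asking questions. This stands, and it limits the finding to what is described. It does not remove the need for action: if an item exists, the plan still has to name it, with its timing and coding, before analysis.

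Second, H6 is not among the primary endpoints in section 8.1, does not drive the sample size in section 11.2, and is not spelled out in the text of Aim 3 in section 1.1. This also stands. The primary comparison is unaffected, and withdrawing H6 would be a legitimate way to restore consistency.

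Third, a new item brings its own problems. Nurse contact prompted by an IVR report occurs only in the intervention arm, and patients who do not fill or who stop the drug have fewer interviews (sections 7 and 22.4), perhaps unequally by arm. Counting a yes at any follow-up interview would leave out patients whose baseline interview is final and would give the others unequal opportunity. These points are sound and shape the fix.

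**Conclusion.** The concern holds in this form: H6 is promised a between-arm test, and no measure described in section 9.4 records in both arms whether patients communicated questions about their prescription. The size is one of the four Aim 3 hypotheses left without a usable between-arm outcome. This should be corrected, but it does not threaten the primary analysis.

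The conclusion assumes that section 9.4 fairly summarizes the interview content. A reader might go further and infer that no interview asks about this, that none of the planned 1200 patients will have H6 data, or that H6 cannot be tested at all. The documents do not support those statements, because the instruments are not shown. Nor do they support the inference that the IVR is the only place where patients' concerns are recorded, since the interview probe in section 9.4 is another; or that charts are definitely closed to the study, since sections 25.3 and 11.2 disagree.

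**What to change.** Add to the interviews or, if the battery already contains one, name in section 9.4 a single item worded identically in both arms: whether the patient has asked the prescriber, nurse or pharmacist a question about the study drug since it was prescribed (yes/no). Include it in whichever interview is final under section 22.4, including baseline. State that calls to the study IVR do not count, and that nurse contacts started by the clinic after an IVR report do not count.

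In section 11.1, define H6 as the response at the final completed interview. The alternative is a yes at any interview where the item was asked, reporting the number of interviews by arm. Compare the arms with clinic clustering accounted for; the logit-link mixed model with practice location as a random effect, already specified for Aim 1, could be used in place of an unadjusted chi-square test.

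If no item is added or named, remove H6 from the H4-H7 comparison.

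The cost is a slightly longer telephone interview, the Spanish translation of one item, and short additions to sections 9.4 and 11.1.

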2. BACKGROUND

2.1 Relevant prior experience and gaps in current knowledge

Research has repeatedly demonstrated that individuals lack essential information on how to take prescribed (Rx) medications safely. Knowledge deficits are greatest for information pertaining to risks and warnings. Inadequate patient knowledge has been cited as a root cause of unintentional misuse, which can lead to serious adverse drug events. This is not surprising, as neither prescribing clinicians nor pharmacists routinely counsel patients on medication risks and safe use. Instead, patients heavily depend on product labeling, such as package inserts, container labels, leaflets, and Medication Guides – all of which are limited in their clarity and effectiveness. Our team has found that even when evidence-based, health literacy best practices are employed to these written tools, the elderly and those with low literacy continue to be inadequately informed and are therefore at greater risk for medication errors and/or suboptimal treatment.

Medication errors refer to any mistake made by a provider or patient that occurs during the process of medication use. Adverse drug events (ADEs) are defined as “any injuries resulting from medication use, including physical harm, mental harm, or loss of function.” Medication errors do not necessarily always result in an ADE, but often impact treatment effectiveness. While the exact prevalence of medication errors in ambulatory care is difficult to estimate, nearly 10 million outpatient physician visits and 4 million emergency department admissions are attributed to ADEs or side effects annually. These are more likely to occur in primary vs. specialty care settings, among older patients or those with multi-morbidity. Among adults seen in outpatient practices who take a medication, 16 to 25% experience an ADE over the course of a year. Occurrence of ADEs depends on patient factors and drug class; regardless, most are detected late - if at all. Thus, patients remain at risk for further harm and less effective treatment. From a public health/pharmacovigilance perspective, early detection of ADEs could provide new information on a medication’s safety and inform the care of others taking it.

Root Cause: Patients Lack Sufficient Information to Ensure Safe Use. Poor patient awareness and/or misunderstanding of medication risks and instructions are often cited as an underlying, root cause of medication errors and ADEs. This is not surprising, as patients often lack sufficient information to help support medication use in ambulatory care. Although most patients prefer to receive medication counseling from their physician, doctors often fail to review even basic drug information with patients. Yet patients who receive medication counseling are more likely to be adherent to their regimen. While there are guidelines promoting counseling, physicians receive limited guidance on what specifically to tell patients about drugs. At the point of dispensing, pharmacists also frequently fail to counsel patients on safe medication use, despite federal and state mandates to do so. Pharmacists may not be fully aware of why a patient was prescribed a medication (i.e. indication for use) or what spoken instructions were provided by the physician. With limited spoken counseling or instruction, patients must instead rely on written communication, such as package inserts, container

STU#: 00201638

labels, auxiliary warnings, and leaflets to support safe medication use. Our team and others have found all to be too complex, particularly for patients with limited literacy and/or English proficiency. Literacy, Age, and English Proficiency are Risk Factors. Many studies have found limited literacy skills to be significantly associated with patients' poorer recall of medication names and indications, inadequate understanding of Rx instructions and precautions, and demonstrated Rx misuse. Deficits are often greatest for information pertaining to risks and warnings. Older patients also may be more likely to lack sufficient knowledge to use prescribed medications safely, as they are disproportionately affected by limited literacy, cognitive impairment, and comorbidity. Limited English proficiency (LEP) also presents a formidable challenge to healthcare. Interpreters are rarely available to aid physicians and pharmacists in counseling LEP patients, instructions often are unavailable in non-English languages, and multilingual materials may be poorly translated and inaccurate. The result is higher misuse and non-adherence rates among LEP patients.

FDA Actions: Risk Evaluation and Mitigation Strategies and Medication Guides. The 2007 FDA Amendments Act (FDAAA) expanded the FDA's authority to require drug manufacturers to submit Risk Evaluation and Mitigation Strategies (REMS) for medications deemed to possess serious public health concerns in order to ensure product benefits outweigh known risks. REMS include: 1) Medication Guides (a.k.a. Med Guides) - print patient materials that highlight a drug's safety information and are required to be distributed to all patients receiving the medication; 2) Communication Plans - strategies to educate providers on safe, appropriate use, and how to counsel patients; 3) Elements to Assure Safe Use - other assurances for proper prescribing (i.e. physician certifications, patient registries), and 4) Evaluations of REMS Performance - periodic reporting to FDA on whether REMS components have achieved goals. To date, over 400 drug products have been required to include a Med Guide or Communication Plan as part of REMS.

Med Guides are the only mandated assurance that patients receive tangible safety information for a prescribed medication prior to use, potentially preventing ADEs and allowing patients to remain vigilant during use. A prior study by Shrank and colleagues found that Med Guides were rarely distributed to patients by pharmacies as required with prescriptions. This is understandable, as many pharmacies cannot embed Med Guides within their electronic record, therefore dissemination depends on the pharmacist remembering that a drug requires a Med Guide and physically retrieving the Guide for the patient. In another study by our team, only 1 in 4 patients reported ever reviewing Med Guides dispensed with Rx drugs. We also found that patient comprehension of existing Med Guides was extremely poor. While older adults and those with lower literacy were less able to understand Med Guides supporting safe use, all patients had considerable difficulty.

Yet the REMS requirement under Communication Plans (to educate and prepare providers on medication risks and patient counseling) is equally flawed. The current practice for drug manufacturers is to identify their 'prescriber pool' through provider ID numbers and collect a mailing list from state licensure boards. Physicians and other clinicians therefore receive letters in the mail from the manufacturer, which rarely are attended to by the recipient. The result is that neither prescribers nor patients are adequately informed about medication risks.

Inadequate provider counseling and print information explains why many patients are unaware and inattentive to drug risks. Poor knowledge and insufficient vigilance is likely to increase the risk of errors and ADEs. This is of greatest concern for older patients and those with limited literacy or LEP.

A Health Literacy Approach to Patient Medication Information. The FDA has acknowledged the complexity of Med Guides and is actively investigating ways to improve them and other tangible sources of patient medication information. In July 2014, the FDA sponsored a Brookings Institution public workshop to consolidate health literacy research in this area and identify future directions. Guidance from a number of fields of study (communication, education, human factors, cognitive

STU#: 00201638

psychology) helped set forth best practices for developing health information to optimize comprehension. In particular, our team developed and evaluated an evidence-based, 'low literacy', 1-page Med Guide Summary to accompany the longer, FDA-required Med Guide, to promote patient understanding of risk information. We conducted a clinical trial among 1003 primary care patients to test the effectiveness of this summary sheet. We found that that our Med Guide Summary (see Preliminary Studies) significantly improved patients' ability to retrieve and apply medication information. This was uniformly seen among patients across all literacy levels and ages. Despite this success, our results underscored the limitations of using only a print modality to convey important health information. More than a third of individuals with marginal literacy and over half with low literacy still struggled to understand information contained in the Med Guide Summary; none of the prototypes achieved >80% comprehension rates (a target threshold for patient education materials). More aggressive strategies beyond written materials are warranted to ensure all patients are adequately informed in support of safe medication use.

The Need for a Primary Care-Based Response. In primary care, many of the medications commonly prescribed have REMS and Med Guide requirements. Few if any mechanisms, however, exist to ensure and confirm patients receive easy-to-understand risk information. The ability to routinely monitor patients' actual use of these higher-risk medications is also not presently possible. Instead, physicians often rely heavily upon patients, both to learn independently about their prescribed medication and to inform their provider of any errors, ADEs, or adherence concerns. Frequently, clinicians do not learn of any medication problems, or only hear of such issues later at the next follow-up encounter. This is problematic, as many patients, especially those with limited literacy or taking multiple medications, have difficulty linking side effects to signs of a potential ADE and may be unaware of the need to contact their physician. In one study, 37% of ameliorable ADEs were attributed to patients not informing their provider of signs and symptoms.

To date, most initiatives to reduce ADEs have focused exclusively on physician prescribing practices. Yet most ADEs do not result from poor prescribing decisions, but from side effects experienced from an appropriately prescribed drug. As many as half of ADEs can be detected and mitigated at an early stage, making opportunities for amelioration up to 2.5 times as likely as opportunities to prevent ADEs through better prescribing. We will address current shortcomings by promoting: 1) provider counseling, 2) dissemination of understandable, actionable medication risk information, and 3) routine surveillance of medication use in primary care by using available health technologies to 'hardwire' medication communication and surveillance of higher risk medications.

